2.3 Preliminary Data

Our Tanzanian colleagues conducted a preliminary study with similar research design over 12 months from March 2013 to February 2014. Fifty-four patients with Gustilo and Anderson Type 3A tibial shaft fractures were enrolled and randomly allocated to two treatment groups. Twenty six were treated with definitive external fixation, and 28 were managed with intramedullary nailing. Two patients were lost to follow-up from each group, leaving a total study population of 50 patients followed for 4.5 months.

As previously stated, the most common mechanisms of injury included motorcycle collisions (75.8%) and motor vehicle collisions (20.4%), followed by bicycle accidents and falls from height (combined 3.8%). Young men were most commonly affected. More than 60% of patients were treated within 16 hours from injury and 98% were treated within 24 hours from time of injury. Patients were treated according to standard open fracture protocols and randomized to two treatment groups undergoing either intramedullary nailing or external fixation.

We found no statistically significant difference in the rates of wound healing or incidence of deep infection (7.7% for IMN vs 12.5% for ex-fix). Twelve patients (46.2%) treated with external fixators developed superficial infection, none of which required implant removal. We observed a significantly faster time to callus formation in the intramedullary nail group (average 8.15 +/- 2.5 weeks, 92% at 10 weeks) when compared with the external fixation group (14.7 +/- 3.3 weeks, 25% at 10 weeks). Patients treated with intramedullary nails attained full weight bearing earlier than pts treated with external fixators. Malunion rates were also significantly lower in the intramedullary nail group, as two ex-fix patients (8.3%) were found to have significant post-operative limb length discrepancies and three (12.5%) were revised for angular or rotational malalignment, versus no malunions noted in the intramedullary nail group.

In summary, 9 patients (37.5%) treated with external fixation required re-operation (2 for deep infection, 3 for malalignment, 4 for delayed union) versus one re-operation (3.8%) for patients treated with intramedullary nailing. While early results from this pilot study predict a clinical advantage for intramedullary nailing over definitive external fixation, we feel the small sample size, limited follow-up, and lack of functional outcomes data warrant further empirical investigation. Most importantly, this pilot study, conducted by a Tanzanian primary investigator, demonstrates the viability of success for completing a larger randomized, prospective clinical trial in Dar es Salaam, Tanzania.

3. Specific Aims

Study Objective: To determine the optimal management of severe open tibial fractures in Sub-Saharan Africa in order to reduce long-term disability, limit the economic impact of injury, and avoid resource costs of reoperation.

Specific Aims

1) Compare the all-cause reoperation rate for AO/OTA Type 42 open tibial shaft fractures treated with initial intramedullary nailing versus external fixation at Muhimbili Orthopaedic Institute in Dar es Salaam, Tanzania.

- 2) Compare rates of secondary clinical endpoints including postoperative superficial and deep infection, clinical union, radiographic union, malunion, and health-related quality of life with minimum one year follow-up.
- 3) Identify prognostic factors related to the patient, injury, or management protocol that impact the reoperation rate, return to work, and health-related quality of life.

Study Null Hypothesis: There is no difference in the all-cause re-operation rate comparing reamed intramedullary nailing and external fixation for the initial treatment of OTA 42 Type 42 open tibia fractures

4. Methods

The proposed study will be a prospective, randomized trial conducted at Muhimbili Orthopaedic Institute (MOI) in Dar es Salaam, Tanzania. All skeletally mature patients presenting to the emergency department between December 2015 and December 2016 meeting inclusion criteria will be consented and enrolled in the study. Baseline clinical data will be obtained during enrollment. The patients will then undergo a standard wound debridement protocol (regardless of treatment arm) followed by intraoperative confirmation that the wound can be primarily closed. If so, the patient will be randomized using the REDCAP randomization module to one of two treatment arms: intramedullary nailing or external fixation. Primary and secondary outcomes will be measured prospectively during the postoperative period and at subsequent follow-up visits at 2wk, 6wk, 3mo, 6mo, and 1yr (Sections 2.6 and 2.7). Serious adverse events that occur during the study will be presented to all co-investigators (Section 3.2). Interim analysis will be produced and reviewed by all co-investigators every 6 months, with a final report generated within three months of the trials end (Section 2.9 and 3.3).

UCSF-MOI Open Tibia Study Overview

[figure not shown]

Figure 1: Timeline for patient enrollment and data collection

4.1 Outcomes

The primary outcome for our study will be composite, all-cause reoperation within one year of definitive skeletal stabilization, excluding bedside irrigation and debridement for superficial pin tract infections or planned ex-fix removal. The use of composite outcomes has been validated in a wide range of clinical trials.¹⁹ Primary events included in our composite outcome are detailed in the following table.

A participant who undergoes conversion from ex-fix to nail within six weeks of surgery will be analyzed according to the initial treatment that was assigned by randomization. Patients who undergo conversion from ex-fix to nail more than six weeks after the index procedure will be considered to have undergone a reoperation and will therefore count toward the primary outcome. Conversion from nail to ex-fix, regardless of time point, will be considered a primary outcome event.

Primary Events

Infection or hematoma	Repeat incision and debridement or drainage for superficial or deep infection or hematoma following initial wound healing.
Bone grafting	Bone grafting for patients > 6 months from index surgery. Bone grafting will be considered after 6 months in the case of delayed radiographic healing with > 2 months pain on attempted weight bearing.
Implant conversion (e.g. Ex Fix to IM nail) or implant exchange (e.g. exchange nailing)	Implant conversion or implant exchange > 6 months from index surgery to facilitate union.
Implant removal	
 1) For construct failure with appropriate clinical indication (broken hardware, half-pin failure at bone/pin interface). 2) Intramedullary nail removal to facilitate union. 3) Intramedullary nail removal due to patient reported pain or local irritation
Dynamization of intramedullary nail	
To facilitate healing > 6 months from index surgery.
 
* Note: Auto-dynamization without clinical indication for removal of broken component will not be counted as a primary event.

Osteotomy	To correct malalignment
Amputation	For limb salvage failure

Secondary clinical outcomes will include:

1. Post-operative compartment syndrome.
2. Superficial infection, as defined by CDC surveillance definitions, to include pin tract infections and cellulitis which resolves with use of antibiotics and local wound care.
3. Deep infection, as defined by CDC surveillance definitions, to include deep abscess or osteomyelitis.

4. Clinical union of fracture healing will be assessed by absence of movement at fracture site and time to painless weight bearing.²⁰ Non-union will be defined as fracture failure to heal beyond six months from date of injury.
5. Radiographic union will be assessed using rate of callous formation and visibility of fracture line as measured by the RUST score.²¹
6. Malunion. Post-operative malalignment will be defined as leg length discrepancy (>1 cm shortening), angular malalignment (> 5 degrees sagittal or coronal angulation referenced contralateral leg radiographs, if non-injured), or malrotation (>10 degrees, determined by Foot-Thigh Angle).
7. Implant failure will be defined as breakage or loosening of any implant component at bone-implant interface which necessitates re-operation.

Secondary functional outcomes will include:

1. Health-related quality of life as measured by EQ-5D.
2. VAS pain score.
3. Knee and ankle range of motion.
4. Functional testing to include walking speed and ability to assume full crouch.

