5.5 Damage Control

After assessing the wound, the primary surgeon will need to determine if “damage control” using a temporary external fixator is necessary. This may be utilized in situations where the patient is hemodynamically unstable and needs quick stabilization of the tibia or requires another surgery that is more important. This option is available to the surgeon for both RCT and cohort patients. Furthermore, this option is available for RCT patients who are randomized to either a nail or an exfix.

If the surgeon decides to perform damage control, a temporary external fixator will be placed, and the patient will be allowed to recover in the ward with the definitive operation performed at a later date. The date of both the temporary exfix placement and the definitive operation will be recorded onto REDCAP. There is no set time limit or criteria for how long the temporary external fixator should remain on before the definitive treatment is to be conducted. The only standardized policy is that the definitive operation should take place in a timely manner after the clinical issue that warranted the temporary external fixator in the first place has been resolved.

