5.7 Definitive Treatment

Nail: It is up to the surgeon’s discretion as to the appropriate size of the nail. A total of 4 screws will be placed – 2 proximal and 2 distal. These decisions will be recorded on REDCAP during the operation.

Exfix: Two Schanz screws will be placed proximally and two will be placed distally; only a single bar will utilized. The patient will be instructed on proper pin-care procedures at the time of discharge which involves pouring methylated spirit (alcohol) directly onto the pins twice daily until the exfix is removed. The patient will be discharged with bandages covering the wound, but the pin insertion sites will be left open to allow for proper ventilation and pin-care. The patient will be discharged with dressing covering the wound and pin sites. The exfix will remain on for 3 months. At the 3 month follow-up, the decision will be made to (1) remove ex-fix, (2) remove ex-fix and replace with cast, (3) delay exfix removal, or (4) other. Delayed removal or other will be submitted for adjudication review.

Wound Protocol

If the wound is dry at the 2 week wound check, the dressing will be removed. If the wound is still wet at 2 weeks, the dressing will be changed and the patient will be instructed to periodically revisit the hospital to change the dressing until the wound becomes dry.

Weight Bearing Protocol

All patients will be advised to be on toe-touch status for the first 6 weeks. Afterwards, the patient will be instructed to bear weight as permitted by pain.

Summary of Treatment Options

Primarily closeable?	->	No	->	Cohort Study
	->	Yes (Cohort) (+ damage control)	->	Temporary exfix
	->	Yes (Cohort) (no damage control)	->	Definitive operation
	->	Yes (RCT): Nail (+ damage control)	->	Temp exfix (then nail)
	->	Yes (RCT): Exfix (+ damage control)	->	Temp exfix (then exfix)
	->	Yes (RCT): Nail (no damage control)	->	Nail now
	->	Yes (RCT): Exfix (no damage control)	->	Exfix now

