5.10 Adjudication Review

Review of the following study events will require review from the members of the study steering committee:

1. Death of a patient
2. Delayed external fixation removal
3. Surgical complications requiring reoperation

The review, comment, and voting process will occur on REDCAP. 3 steering members will need to evaluate each event that is put up for review. The steering committee members are responsible for providing the following inputs for each event:

1. Comments/opinions/justifications
2. Vote (yes or no): question varies depending on the event
 - a. Death event: question not applicable
 - b. Delayed external fixation: does the patient need to remain on external fixator for an extended length of time?
 - c. Surgical complications requiring reoperation: does the patient need a reoperation?
3. Vote (yes or no): is this event a primary outcome of the study?

Adjudication review will be conducted every 2 months.

Final Reporting

At the conclusion of the study there will be a principal manuscript reporting the findings of the primary study endpoints.

On-Duty Schedule and Responsibilities

A research coordinator is required to be on duty at all times. A person will remain on-duty for three consecutive days. The transition to the next person on duty will occur at noon or in the early afternoon after the person on-duty has finished the morning tasks. During the transfer, the person on duty should notify the next person on duty about any pending items that need to be completed. These items should be written down in the on-duty diary.

Scheduling of the person on duty is to be done on an excel form available in the dropbox. Substitutions are permitted as necessary. The form is to be maintained and updated should any substitutions occur.

The following need to be provided for the on-duty coordinator:

- Study Laptop and USB Modem
- Study Phone
- Battery charge bank and wire
- On-call diary
- SIGN office key
- Antibiotics
- Wound measurement ruler
- On-duty diary

- Extra forms: consent, OTA wound classification, EQ-5D

Daily tasks for on-duty

To do in the morning:

- Patients in ward: (1) create follow-up schedule and (2) make sure they receive their antibiotics
- Patients in emergency: periodically check to see if there are any new patients
- Check in emergency logbook if there were any missed patients
- Patients waiting for operation: wait and randomize in OR
- Get the unused antibiotics from emergency room from last night

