The patient **IS** eligible for the RCT but has been enrolled in the COHORT study. Because of this, the randomization window module will not appear.

Please double check the inclusion/exclusion criteria. Do not proceed until this error has been resolved.

- b. For RCT patients, this is what the randomization module appears like. Click on randomize, confirm the warning message, and randomize the patient. The randomization module results are final. Once randomization has been performed, the patient must remain in the study and must receive that operation

THIS IS THE RANDOMIZATION MODULE. ONCE YOU RANDOMIZE, THE RESULTS ARE FINAL

This patient has been randomized to receive:

* must provide value

Date and Time of Randomization

* must provide value

Insert date and time by clicking on the calendar image above

4. Damage Control

- a. If the patient believes that damage control using a temporary external fixator should be performed before the definitive operation that the patient has been randomized to (in the case of RCT patients) or that the surgeon has decided (in the case of cohort patients), then record "Yes". Damage control is usually done in situations where the patient is not hemodynamically stable enough for a full surgery, but it is still better to temporarily fixate the fracture using an exfix.

Variable: random [Branching logic exists]

THIS IS THE RANDOMIZATION MODULE. ONCE YOU RANDOMIZE, THE RESULTS ARE FINAL

This patient has been randomized to receive:

* must provide value

Date and Time of Randomization

* must provide value

Will the surgeon perform "damage control" using an external fixator because the patient is currently too unstable?

* must provide value

The patient will now receive a temporary external fixator and receive the definitive operation at a later date. This is allowed under our study protocol.

Please remember to record the dates of both operations in the post-op/discharge form.

reset

5. At this time, additional antibiotics can be added or removed depending on how much contamination the surgeon believes there to be inside the wound

Does the surgeon believe additional antibiotics are required?

+ Gentamycin
 + Gentamycin + Metronidazole
 Other
 No

If "Other", please describe the following:

- Type of antibiotic
- Dosage
- Timing

Expand

6. Wound Characteristics

- Record the wound measurement details here in centimeters
- OTA wound classification performed by surgeon

Wound Measurement	

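### The primary-outcome rule in section 4.1 leaves early events in damage-control patients uncounted, contradicts itself on ex-fix-to-nail conversion, and has no end-of-year check for patients seen early (minor)

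*Protocol*

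**What the plan says.** **Start of the clock.** Section 4.1 counts "all-cause reoperation within one year of definitive skeletal stabilization". Section 4 places randomization earlier, after "intraoperative confirmation that the wound can be primarily closed. If so, the patient will be randomized using the REDCAP randomization module". Section 5.5 allows temporary external fixation (damage control) in randomized patients of either arm, and says of it: "There is no set time limit or criteria for how long the temporary external fixator should remain on". The treatment summary in section 5.7 accordingly shows a two-stage path in each arm: temporary fixator then nail, and temporary fixator then definitive fixator. On the form in section 6.2 the randomization item precedes the damage-control item, whose message reads "The patient will now receive a temporary external fixator and receive the definitive operation at a later date".

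**Conversion.** The text of section 4.1 counts as a reoperation a "conversion from ex-fix to nail more than six weeks after the index procedure". The Primary Events table in the same section has "Implant conversion or implant exchange > 6 months from index surgery to facilitate union". The section also uses *surgery*, *index procedure* and *index surgery* without saying which operation each means when there are two.

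**End of the clock.** Section 5.8 makes the 1-year visit the last one and rounds the schedule to Saturdays. The scheduling table in section 6 puts that visit at day 364 with a window of -35/+120 days. End-of-year contact in section 5.8 is for patients lost to follow-up. Section 6.6 accepts complications that patients report outside clinic and keeps a report of reoperations still awaited.

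**Adjudication.** Under section 5.10 three steering committee members vote on each reviewed event: "is this event a primary outcome of the study".

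**The concern.** A comparison of randomized arms should cover the course that follows randomization. Here the outcome clock of a damage-control patient opens at a later operation, and the decision that delays it is recorded when the allocation is already visible. Section 6.2 says a randomized patient must remain in the study, yet a patient who dies or loses the limb before the definitive operation has no outcome window at all.

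The undefined index terms matter because they can act on one arm only. If *index procedure* means the temporary fixator, a planned nail placed more than six weeks later meets the conversion sentence as written and scores as a failure in the nail arm. A planned second fixator in the other arm is not a conversion to a nail and cannot score that way. The two conversion thresholds add a second ambiguity: between six weeks and 6 months the text counts a conversion and the table does not.

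At the other end, some event types (bone grafting, implant conversion or exchange to promote union, dynamization) count only after 6 months. If the last scheduled contact comes early, part of the period in which they can score rests on what patients report themselves.

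**Working it through.** **1. Which events can fall in the early gap.** From the Primary Events table in section 4.1:

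| Component | Can it score between randomization and definitive surgery? |
|---|---|
| Infection or hematoma | Rarely: only after initial wound healing |
| Bone grafting, union-related conversion or exchange, dynamization | No, unless the gap exceeds 6 months |
| Construct failure | Yes |
| Amputation | Yes |
| Osteotomy for malalignment | Not excluded by timing, but unlikely so early |

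The frequency of damage control is not given, so no count or direction of bias follows.

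**2. Earliest 1-year visit.** Inputs: day 364, early limit 35 days (scheduling table, section 6) and the Saturday rounding (section 5.8). The anchor moves to the previous Saturday for Sunday to Tuesday operations and to the upcoming Saturday for Wednesday to Saturday. I take a Saturday operation as anchored on the same day.

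Earliest visit = 364 - 35 + shift; gap = 365 - earliest visit.

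| Operation day | Shift | On-time visit | Earliest visit | Gap |
|---|---|---|---|---|
| Sun | -1 | 363 | 328 | 37 |
| Mon | -2 | 362 | 327 | 38 |
| Tue | -3 | 361 | 326 | 39 |
| Wed | +3 | 367 | 332 | 33 |
| Thu | +2 | 366 | 331 | 34 |
| Fri | +1 | 365 | 330 | 35 |
| Sat | 0 | 364 | 329 | 36 |

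The mean gap is 36 days: 36/365 = 9.9% of the year, or 36/182 = 19.8% of the half-year after month 6. The scheduling text permits visits outside the window but does not prefer them, so the early edge is not a hard limit.

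**3. The plan's own sample size.** Section 4.2 states 5% vs 20%, alpha 0.05, 80% power, 88 per arm. With two-sided alpha (assumed), the pooled-variance formula gives n = 75.1. The continuity correction gives 75.1/4 x (1 + sqrt(1 + 4/(75.1 x 0.15)))^2 = 87.9, so 88. The figure is reproduced.

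**4. Illustration of power.** The 192 expected completers are 96 per arm. Let d be the rate difference and p the mean rate. Inverting the correction gives n' = N - 2/d + 1/(N d^2), and power = Phi[(d sqrt(n') - 1.96 sqrt(2p(1-p))) / sqrt(p1 q1 + p2 q2)]. With no loss, n' = 96 - 13.33 + 0.46 = 83.1 and power is 83.9%.

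Both rates are then multiplied by 1 - (share seen at day 329) x (fraction of event time lost). This assumes that nothing is reported after the visit and nothing is already flagged at it.

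| Assumed share at earliest date | Event timing | Rates | Power, 96 per arm |
|---|---|---|---|
| none | any | 20% vs 5% | 83.9% |
| 25% | uniform over the year | 19.5% vs 4.9% | 82.7% |
| 25% | all after month 6 | 19.0% vs 4.75% | 81.4% |
| 100% (upper bound) | uniform over the year | 18.0% vs 4.5% | 78.6% |
| 100% (upper bound) | all after month 6 | 16.0% vs 4.0% | 72.1% |

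Planned events among 192 are 96 x 0.05 + 96 x 0.20 = 24. At 25% early attendance the loss is 24 x 0.25 x 9.9% = 0.6 to 24 x 0.25 x 19.8% = 1.2 events.

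**The case against.** Starting at definitive fixation is a defensible choice: it keeps the planned second stage of damage control from scoring as a reoperation. It also moves the end of the window later, so it is not a pure loss. That stands, and it rules out the simple remedy of a window from randomization to day 365, which would add early days with few qualifying events and drop late days when grafting, union-related exchange and dynamization can score.

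A reader might infer that section 4.1 gives adjudicators no time origin. It does: definitive stabilization, and section 6.4 records both operation dates. Only the index terms are loose, and the three-member vote limits the harm.

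A reader might also infer that the allocation is biased through damage control, or that the primary comparison is underpowered. The documents support neither. They give no damage-control frequency and no difference between arms, and no passage suggests that early attendance is common. A visit is moved when the patient cannot come on a given Saturday, and the window is wider late than early. An early visit would also flag many pending reoperations. It includes radiographs, asks about pain on weight bearing and about nonunion, and anything under consideration goes on the awaited-reoperation report. Under section 4.1 grafting requires more than 2 months of pain, so a graft by day 365 implies pain from about day 305 (365 - 60), before the earliest in-window visit. The table in the working credits none of this.

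The February 2016 entry in the summary of changes gives two weeks for definitive treatment after damage control. If that limit held in practice, the early gap would be short. Its difference from section 5.5 is not counted as an error here, because that log may describe superseded text.

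An analysis plan, not shown, might handle patients without a definitive operation. It could not recover reoperations that were never ascertained, and the event definitions are fixed in this protocol.

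**Conclusion.** The point holds as a minor one, in three parts. First, in damage-control patients a qualifying event between randomization and definitive surgery is outside the primary outcome, and a patient who never reaches that surgery has no start date; few event types can fall there. Second, the primary-event rule is wrong as written: the two conversion passages in section 4.1 disagree, and the undefined index terms allow a reading under which a planned late nail scores in the nail arm only. Third, an in-window early visit leaves 33-39 days without a scheduled check, so a new reoperation in that time depends on patient report.

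The number of missed events cannot be derived and is probably small. The fall in power from 84% to 81-83% is an illustration that rests on 25% attending at the earliest date, equal attendance in both arms, and no later report. Only the implausible bound with every patient seen early takes power below 80%.

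**What to change.** 1. In section 4.1, count qualifying events from randomization through one year after definitive stabilization, or through one year after randomization if that stage is never reached. Keep the present exclusions and add the planned definitive stage of damage control in both arms. Cost: wording, and a window longer by the damage-control delay in those few patients.
2. State which operation *surgery*, *index procedure* and *index surgery* mean in two-stage patients, and reconcile the six-week and 6-month conversion passages. Which threshold applies is for the investigators to settle. Cost: wording.
3. In REDCap, record the damage-control decision before the randomization button and log any later change with its reason. Cost: a change in field order and an occasional log entry.
4. For anyone whose last contact precedes the end of the outcome year, make one phone or record check for reoperation on or after that date, and count only events inside the year. Cost: a few calls. Section 5.1 opens screening on 14 December 2015 for about a year and section 4.3 completes follow-up in December 2017, so most checks fit. If enrolment is extended, as section 4.2 allows, or the definitive operation is delayed, the checks move with it.

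### Section 4.1 counts nail-to-ex-fix conversion at any time but, by implication, ex-fix-to-nail only after six weeks, so early conversion is scored differently by arm

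*Protocol*

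**What the plan says.** Protocol 4.1 defines the primary outcome as "composite, all-cause reoperation within one year of definitive skeletal stabilization, excluding bedside irrigation and debridement for superficial pin tract infections or planned ex-fix removal". Three sentences on conversion follow:

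- On early ex-fix-to-nail conversion: "conversion from ex-fix to nail within six weeks of surgery will be analyzed according to the initial treatment that was assigned by randomization".
- On the same change made later: "conversion from ex-fix to nail more than six weeks after the index procedure will be considered to have undergone a reoperation". These patients therefore add to the primary outcome.
- On the reverse change: "Conversion from nail to ex-fix, regardless of time point, will be considered a primary outcome event".

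The Primary Events table in the same section has its own row for conversion: "Implant conversion or implant exchange > 6 months from index surgery to facilitate union". That row gives no direction.

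Protocol 5.5 allows a temporary ex-fix for damage control in both arms: "this option is available for RCT patients who are randomized to either a nail or an exfix". The summary of treatment options in 5.7 shows where that stage leads. In the nail arm the temporary frame is followed by the nail. In the ex-fix arm the path is "Yes (RCT): Exfix (+ damage control) -> Temp exfix (then exfix)".

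Protocol 5.10 has three steering committee members vote on whether each reoperation is a primary outcome. It gives them no rule on conversion.

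**The concern.** Take two patients at week 3 after definitive fixation. One has an ex-fix replaced by a nail, the other a nail replaced by an ex-fix, both unplanned. Both have had a second operation to replace the allocated implant with the other one. The text makes the second an event. For the first it states the analysis arm and leaves the reader to infer, from the sentence that follows, that there is no event.

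This conflicts with the all-cause label, because early conversion is not among the two exclusions. It also works in one direction only: it can lower the counted rate after external fixation and has no counterpart after nailing. The operating surgeon knows the implant, and 2.3 says the pilot results favour nailing, so some early conversion out of the ex-fix arm is plausible. The planned contrast rests on few events, so a handful of uncounted operations would matter.

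**Working it through.** **1. How the passages score the same operation.** Unplanned change of the definitive implant, after definitive fixation:

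| Operation | Conversion sentences in 4.1 | Implant-conversion row of the table |
|---|---|---|
| Ex-fix to nail, week 3 | Arm stated; by implication no event | Not counted |
| Nail to ex-fix, week 3 | Event | Not counted |
| Ex-fix to nail, month 3 | Event | Not counted |
| Nail to ex-fix, month 3 | Event | Not counted |
| Either direction, month 8 | Event | Event, if done to promote union |

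The arms differ only in the first two lines. The table row conflicts with the text in lines 2 to 4. Choosing one late threshold for ex-fix-to-nail conversion would not by itself remove the early difference while the nail-to-ex-fix sentence stands.

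**2. Whether the exemption could also remove nail-arm events.** A nail-arm patient may have a temporary frame and then the nail. The outcome clock in 4.1 starts at definitive stabilization, which for that patient is the nailing, so there is no event to exempt. In the ex-fix arm, 5.7 gives no planned path to a nail. What the early window exempts there is therefore unplanned conversion.

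**3. The plan's own sample size.** Inputs from 4.2: rates of 5% and 20%, alpha 0.05, power 80%. The sentence does not name the arms; the order of the pilot results implies nail 5% and ex-fix 20%. Two-sided testing is assumed. With mean rate 0.125:

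n = [1.96·√(2·0.125·0.875) + 0.8416·√(0.05·0.95 + 0.20·0.80)]² / 0.15² = (0.9167 + 0.3834)² / 0.0225 = 75.1, so 76 per arm.

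With continuity correction: n = (75.1/4)·[1 + √(1 + 4/(75.1·0.15))]² = 87.9, so 88 per arm. This is the protocol's figure.

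**4. Illustration of the effect.** Assume the true rates are the planning rates, early conversions are part of the 20%, and a share e of ex-fix patients has an early conversion as the only reoperation and it goes uncounted. The counted ex-fix rate is 0.20 − e and the counted difference is 0.15 − e. Power at 88 per arm is Φ[(difference − 1.96·SE₀)/SE₁], where SE₀ uses the pooled rate and SE₁ the separate rates; the corrected version subtracts 1/88 from the difference.

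| e (points) | Counted ex-fix rate | Difference (points) | Power, corrected | Power, uncorrected | n per arm for 80%, corrected |
|---|---|---|---|---|---|
| 0 | 20% | 15 | 80% | 86% | 88 |
| 1 | 19% | 14 | 75% | 82% | 98 |
| 2 | 18% | 13 | 70% | 78% | 109 |
| 3 | 17% | 12 | 64% | 72% | 122 |
| 4 | 16% | 11 | 57% | 67% | 139 |
| 5 | 15% | 10 | 50% | 60% | 160 |

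For e = 3: pooled rate 0.11, SE₀ = √(2·0.11·0.89/88) = 0.0472, SE₁ = √[(0.05·0.95 + 0.17·0.83)/88] = 0.0463. Uncorrected: (0.12 − 0.0925)/0.0463 = 0.595, power 72%. Corrected: (0.12 − 0.0114 − 0.0925)/0.0463 = 0.350, power 64%.

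In patients, 3 points of 88 is 2.6, against expected counts of 17.6 (0.20·88) and 4.4 (0.05·88). If all 192 patients hoped for in 4.2 are analysed (96 per arm), 3 points lower power from 84% to 68% corrected, or from 89% to 76% uncorrected.

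**The case against.** The strongest points on the other side are these.

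- **Non-counting is not stated.** The six-week sentence fixes the analysis arm and nothing more. Under the all-cause definition an early conversion could still be read as countable. This stands: the defect is partly one of wording. But the next sentence counts conversion only after six weeks, and the event status of an operation in the primary outcome should not be left to inference.
- **Other routes may capture early conversions.** Table rows for construct failure, infection and osteotomy carry no six-week or six-month limit. The follow-up form in 6.5 flags an ex-fix plan that includes conversion as non-standard and sends it to the complications form, and 5.10 sends reoperations to committee vote. This also stands. A reader might infer that surgeons can convert early, unseen and free of any event; the documents do not support that. What these routes lack is a common rule for both arms.
- **Staged care explains the rule.** Section 2.2 describes a temporary frame followed by a planned nail, with no planned stage in the other direction. That explains the wording but does not rescue it, for the reasons in step 2 of the working.
- **The bias is conservative.** At the planning rates it works against the expected nail advantage. That is true, but if the true rates were equal it would make external fixation look better than it is.

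**Conclusion.** The point holds as an arm-dependent scoring rule in the primary outcome, implied rather than stated, and at odds with the all-cause definition. Its size is unknown because the protocol gives no early-conversion rate. The power figures are an illustration that rests on the planning rates, two-sided testing, conversions lying within the 20%, and no other counted event in those patients. The sample size itself reproduces and is not in question.

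Two stronger readings should be resisted. A reader might add every early conversion on top of the 20%; with 10% of the arm converted, that gives 0.20·0.90 + 0.10 = 28% and a 23-point difference from nail. The documents do not support this, because 20% is already a planned reoperation rate. A reader might also say that the trial no longer tests its hypothesis. The null hypothesis in section 3 concerns initial treatment, and analysis by assigned arm preserves that comparison; the fault lies in how events are counted within it.

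**What to change.** In 4.1, state one scoring rule for both directions: any unplanned change of the definitive implant after definitive fixation is a primary event, whatever its date within the one-year window. Exempt only a damage-control stage recorded on the intra-operative form. Amend the implant-conversion row of the Primary Events table to agree, since its six-month limit would otherwise contradict the rule. Give the adjudicators in 5.10 the same rule. Keep analysis by randomized arm, and report the number and dates of early conversions by arm.

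The cost is a wording change in 4.1 and 5.10. The data are already collected: the damage-control decision (6.2), the dates of temporary and definitive operations and the type of definitive operation (6.4), and the date and description of any reoperation (6.6). The downside is that the ex-fix event rate may exceed the planning figure by an amount that cannot be stated in advance. The change concerns scoring only and takes no position on when, or whether, a conversion should be done.
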